the bony crest. Prior to tooth extraction, the clinical measurement stent will be placed and measurements of ridge width and ridge height will be taken and recorded to the nearest 0.5mm. Ridge width will be measured to the nearest 0.5mm using a ridge caliper at a point **approximately 3mm apical to the facial and lingual bony crest** through small holes created in the stent at those locations. Ridge height will be measured to the nearest 0.5mm through two holes in the occlusal aspect of the stent – one hole directly above the facial bony crest and another hole directly above the lingual bony crest. This stent will be retained for use during the subsequent implant placement surgery.

Use of the stent and subsequent measurements are for research purposes, not standard care.

Tooth extraction will be performed as atraumatically as possible. Following tooth extraction, a final determination of enrollment into the study will be conducted based on the integrity of the buccal bone wall plate at the extraction site. If the buccal plate is intact, defined as **no bony dehiscence greater than 50% of the socket depth**, the patient will remain enrolled in the study. Conversely, if the buccal plate integrity has not been maintained (bony dehiscence >50%) the patient will be exited from the study and standard care therapy will be delivered to the patient.

After extraction, the number of bony walls in each socket will be recorded along with the presence of any bony dehiscences or fenestrations. Buccal and lingual flap elevation will be minimized and will extend no more than 2-3mm beyond the bony crest on the facial and lingual surfaces. The buccal plate thickness will be measured using an Iwanson gauge positioned perpendicular to the inner wall of the extraction socket. One beak of the gauge will be placed within the extraction socket 1.0mm apical to the alveolar bone crest. The other beak will be placed on the external bone surface 1.0mm apical to the alveolar bone crest. This buccal plate thickness measurement will be recorded to the nearest 0.1 mm. Measurements taken with the Iwanson gauge are for research purposes, not standard care.

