
To add more populations – select a row, copy & paste
 
Dental patients needing extraction of a non-molar (“single-rooted”) tooth and ridge preservation
	
All individuals in this study population must meet all of the inclusion criteria in order to be eligible to participate in the study
	
All individuals in this study population meeting any of the exclusion criteria at baseline will be excluded from study participation.

	
 • English-speaking patients aged 18 to 90 • One tooth, excluding molars, that has been identified by dental faculty as requiring a single tooth extraction • A dental implant is indicated and treatment planned to replace the missing tooth • Have adequate restorative space for a dental implant-retained restoration • Have at least 10mm of alveolar bone height, without impinging on the maxillary sinus or inferior alveolar canal. • Have a dehiscence of the buccal or lingual bony plate of the tooth socket extending no more than 50% of the total depth of the socket. • Female patients who have undergone a hysterectomy, tubal ligation, or menopause, and non-pregnant women of child-bearing potential. • Are nonsmokers or former smokers. Current smokers may be included if they smoke ≤10 cigarettes per day 	
 • Will not cooperate with the follow-up schedule. • Patients will not be entered who are mentally incompetent, prisoners, or pregnant. • Pregnant women or women intending to become pregnant during the study period (as confirmed verbally; an over the counter pregnancy test will be provided if pregnancy status is unknown or suspected). • Patients who become pregnant during the study will be withdrawn and standard care will be delivered. • Smokers who smoke >10 cigarettes per day • Clinical and/or radiographic determinations which will preclude inclusion in this study are: Active infection other than periodontitis; Inadequate bone dimensions or restorative space for a dental implant; Presence of a disease entity, condition or therapeutic regimen which decreases probability of soft tissue and bony healing, e.g., poorly controlled diabetes, chemotherapeutic and immunosuppressive agents, autoimmune diseases, history of bisphosphonate use or long-term steroid therapy; Positive medical history of endocarditis following oral or dental surgery.

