Randomization of subjects is done through use of envelopes inside which is a piece of paper with the group to which the subject will be assigned. 30 envelopes will be prepared for each of the 4 groups. The envelopes will be sealed and shuffled. The faculty staffing the procedure will draw an envelope from the stack prior to the surgical procedure appointment. Since the outcome of the study is the histologic healing, blinding of the surgeon is not necessary.
Blinding is performed only for histomorphometric measurements. The person doing histomorphometric analysis is blinded as to study group.
10.2. Study Intervention Compliance Define how adherence to the protocol (e.g., administration of study intervention, use of device,) will be assessed, and verified (if applicable, e.g., plasma assays, electronic monitoring devices, daily diaries).
Patients will need to be present at each scheduled visit. Failure to attend visits will result in exit from the study. All providers placing study materials as part of the study intervention will be trained and provided with detailed instructions to ensure methods are consistent and in compliance with the protocol. All faculty staffing residents are familiar with the study protocol and can verify the results of the procedure and measurements taken.
10.3. Permitted Concomitant Therapy This section should be consistent with the medication restrictions in the inclusion/exclusion criteria previously listed. Describe how allowed concomitant therapy might affect the outcome (e.g., drug-drug interaction, direct effects on the study endpoints).
N/A
10.4. Rescue Medicine List all medications, treatments, and/or procedures that may be provided during the study for "rescue therapy" and relevant instructions.
N/A, no rescue medicine

11. Study Intervention Discontinuation
11.1. Discontinuation of Study Intervention Describe the criteria for discontinuing the study intervention (e.g., halting rules), including any monitoring test(s) and associated clinical decision point(s). Include reasons for temporary discontinuation of the study intervention (e.g., type and quantity of adverse events), clearly stating the length of time, if applicable, and describe the data to be collected at the time of study intervention discontinuation and approaches for restarting administration of or re-challenging with study intervention.

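### The post-extraction enrolment check tests the buccal plate only, while inclusion criterion 6.2 limits buccal or lingual dehiscence, so a socket that fails on the lingual side alone is kept by one rule and ineligible by the other

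*Combined protocol and SAP*

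**What the plan says.** Section 5.3, Visit 2, places the last enrolment decision after extraction: "a final determination of enrollment into the study will be conducted based on the integrity of the buccal bone wall plate". The condition for staying in begins "If the buccal plate is intact, defined as" and is completed by a limit of 50% of socket depth on dehiscence. The condition for leaving is "if the buccal plate integrity has not been maintained (bony dehiscence >50%) the patient will be exited from the study".

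Section 6.2 lists as an inclusion criterion: "Have a dehiscence of the buccal or lingual bony plate of the tooth socket extending no more than 50% of the total depth". Patients must meet all "of the inclusion criteria in order to be eligible to participate in the study".

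Visit 2 also says that "the number of bony walls in each socket will be recorded along with the presence of any bony dehiscences or fenestrations", but ties no enrolment decision to that record.

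On timing of allocation, the design summary in Section 5.3 and the later Visit 2 text both put randomization after extraction; the Visit 2 text puts it after debridement of the socket. Section 10.1 says: "The faculty staffing the procedure will draw an envelope from the stack prior to the surgical procedure appointment". Section 12.3 limits the analysis to participants who complete the intervention.

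**The concern.** An eligibility rule should give one answer for a given socket. Here the check that the protocol calls final leaves out one of the two plates that the inclusion criterion names. Different operators could in good faith handle the same lingual defect differently, and each could point to protocol text.

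Two things are at stake. First, the enrolled population may not match the one defined in 6.2, and the omitted wall bears directly on a named secondary outcome, change in lingual ridge height. Second, if the allocation is already known when a lingual defect is found, the choice to keep or exit the patient becomes a possible route for selective exclusion. An exited patient receives standard care instead of the study intervention, so Section 12.3 would leave that patient out of the analysis.

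**Working it through.** No power, sample-size or alpha figure is involved. The check is a comparison of the two rules and then of the statements on allocation timing.

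**Step 1: do the limits differ?** No. Both use 50% of socket depth. The rules differ only in the plates covered.

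**Step 2: compare the rules case by case.**

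| Buccal dehiscence | Lingual dehiscence | Visit 2 check (5.3) | Criterion 6.2 |
|---|---|---|---|
| ≤50% | ≤50% | stays enrolled | meets it |
| >50% | any | exited | fails it |
| ≤50% | >50% | stays enrolled | fails it |

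The rules part only in the third row.

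**Step 3: can the Visit 2 wording be read to cover the lingual plate?** No. The 50% limit there defines when the buccal plate counts as intact, and the exit sentence again refers to buccal integrity.

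**Step 4: does any other text settle the third row?** No. The record of bony walls, dehiscences and fenestrations is taken after extraction but carries no enrolment consequence. It asks for the presence of dehiscences and does not ask for depth as a share of the socket, so a lingual breach of 6.2 could be noted without being measured against the limit.

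**Step 5: when is the allocation known?**

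- Section 5.3 (design summary and Visit 2): randomization follows extraction. In the Visit 2 text it also follows the enrolment check. On this order the keep-or-exit decision is made before allocation.
- Section 10.1: the envelope is drawn before the surgical appointment, hence before the check. The envelopes are sealed, and the section does not say when they are opened.

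Knowledge of allocation at the check therefore requires both that 10.1 is followed and that the envelope is opened when drawn. Section 5.3 states that the surgeon cannot be blinded.

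**Step 6: how many patients?** This cannot be computed. The documents give no frequency of lingual dehiscence above 50% of socket depth.

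**The case against.** The strongest reply is that the two texts are cumulative: 6.2 sets eligibility, and the Visit 2 check is one more test on top of it. On that reading a socket with lingual dehiscence beyond the limit is ineligible throughout. This is a reasonable guess at intent, but Visit 2 calls its check final and says that a patient with an intact buccal plate remains enrolled. The wording still needs correcting.

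Several stronger readings are tempting, and the objection to each stands:

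- *Two conflicting exit rules.* There is one exit rule, at Visit 2. Section 6.2 makes a patient ineligible but describes no exit step.
- *Dehiscence depth can be settled only after extraction.* No section says so. Both flaps are reflected and the facial and lingual crest heights measured before the tooth is removed. The protocol shows only that it places its final buccal decision afterwards.
- *A head count.* Assuming that 2% to 10% of sockets are affected would give 0.02 × 120 = 2.4 to 0.10 × 120 = 12 patients, but the percentages have no source in the documents, so the counts are not evidence.
- *Allocation is known when the rule is applied.* That takes Section 10.1 alone and passes over the two places in 5.3 that randomize after extraction.

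It is also fair to say that the envelope timing is a separate inconsistency: it exposes the buccal decision equally, and aligning the plates would not cure it. If allocation does follow the check, sockets with lingual loss should be spread across arms by chance. Each patient's ridge height is also compared with that patient's own baseline. The expected effect is then some added variability, with no systematic difference between arms.

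**Conclusion.** The inconsistency is real and stands on the text alone. For a socket with buccal dehiscence within the limit and lingual dehiscence beyond it, Section 5.3 keeps the patient and Section 6.2 makes the patient ineligible; nothing else in the document resolves this. It is a minor point. The number of patients is unknown, and no effect on the primary outcome, power or type I error has been shown. The primary outcome is read by an assessor blinded to group. The main consequences are inconsistent eligibility and less clear interpretation of change in lingual ridge height.

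The route to selective exclusion is conditional on following 10.1 and opening the envelope at the draw. The documents support calling it possible. They do not support saying that it will operate or that it biases the comparison. Which plates the limit should cover is for the investigators to decide; this review takes no position on that.

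**What to change.** 1. Reconcile the Visit 2 check in Section 5.3 with criterion 6.2 so that both name the same plate or plates.
2. For each plate named, record dehiscence depth as a share of socket depth, so that the limit can be verified afterwards.
3. State in Section 10.1 that the envelope is drawn and opened only after the enrolment check has been completed and documented. This matches the order already given in Section 5.3.

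The cost is a phrase in one of the two eligibility texts, a sentence in 10.1, and at most one added data field, since the presence of dehiscences is already recorded at that visit. No change to sample size or analysis is needed.

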8.1. Drugs (trade and generic, dosage, route of administration)

N/A

8.2. Devices

Group 1: DFDBA particulate at 125-850 micron size (Vallos)

Group 2: Xenograft (Bio-Oss) combined with DFDBA particulate at 125-850 micron size (Vallomix)

Group 3: DFDBA fibers (Vallos-F)

Group 4: Xenograft (Bio-Oss) combined with DFDBA fibers (Vallomix-F)

8.3. Biologics

N/A

8.4. Laboratory Tests

- If needed: An over-the-counter urine pregnancy test will be provided to female subjects and self-administered in the graduate periodontics clinic of UTHSCSA. A negative result is required to enter the study.
- Histology of the core bone biopsy.

8.5. Imaging Procedures

N/A

8.6. Other Research Procedures (e.g., other safety and efficacy assessments.)

8.7 Attach a Schedule of Activities (SOA) Excel File [Download the Template here: [Schedule of Activities](#)]

Check to indicate that the SOA Excel File is attached →

9. Preparation/Handling/ Storage/Accountability of Investigational Drug, Biologic, or Device

N/A - This study does not include any investigational products (e.g. drugs, devices or biologics)

N/A - An Investigator Brochure is attached

N/A - A Drug/Device Manual is attached

9.1. Acquisition and accountability

State how the study intervention and control product will be provided to the investigator. Describe plans about how and by whom the study intervention will be distributed, including participation of a drug repository or pharmacy, and plans for disposal of expired or return of unused product.

All graft and membrane materials will be provided to the PI via standard shipping. Graft products are provided by Geistlich, Inc. in sterile single-use 1.0cc vials. All 25x25mm BioGide membranes are provided by Geistlich, Inc. in sterile single-use packaging. These materials are all commercially available.

9.2. Formulation, Appearance, Packaging, and Labeling

Describe the formulation, appearance, packaging, and labeling of the study intervention and control product, as supplied. Information in this section can usually be obtained from the IB or the package insert, or device labeling. This section should include the name of the manufacturer of the study intervention and control product.

9.3. Product Storage and Stability Describe storage and stability requirements (e.g., protection from light, temperature, humidity) for the study intervention and control product. For studies in which multi-dose vials are utilized, provide additional information regarding stability and expiration time after initial use (e.g., the seal is broken).
All products can be stored at room temperature. There are no special storage requirements.
9.4. Preparation Describe the preparation of the study intervention and control product, including any preparation required by study staff and/or study participants. Include thawing, diluting, mixing, and reconstitution/preparation instructions in this section. For devices, include any relevant assembly or use instructions.
Products are all used off-the-shelf.

10. Study Intervention Additional Details
10.1. Measures to Minimize Bias: Randomization and Blinding This section should contain a description of randomization and blinding procedures (if applicable to the study design). It should include a description or a table that describes how study participants will be assigned to study groups, without being so specific that blinding or randomization might be compromised. Plans for the maintenance of trial randomization codes and appropriate blinding for the study should be discussed. The timing and procedures for planned and unplanned breaking of randomization codes should be included. Include a statement regarding when unblinding may occur and who may unblind. Provide the criteria for breaking the study blind or participant code. Discuss the circumstances in which the blind would be broken for an individual or for all participants (e.g., for serious adverse events (SAEs)). Indicate to whom the intentional and unintentional breaking of the blind should be reported.
Randomization of subjects is done through use of envelopes inside which is a piece of paper with the group to which the subject will be assigned. 30 envelopes will be prepared for each of the 4 groups. The envelopes will be sealed and shuffled. The faculty staffing the procedure will draw an envelope from the stack prior to the surgical procedure appointment. Since the outcome of the study is the histologic healing, blinding of the surgeon is not necessary.
Blinding is performed only for histomorphometric measurements. The person doing histomorphometric analysis is blinded as to study group.
10.2. Study Intervention Compliance Define how adherence to the protocol (e.g., administration of study intervention, use of device,) will be assessed, and verified (if applicable, e.g., plasma assays, electronic monitoring devices, daily diaries).
Patients will need to be present at each scheduled visit. Failure to attend visits will result in exit from the study. All providers placing study materials as part of the study intervention will be trained and provided with detailed instructions to ensure methods are consistent and in compliance with the protocol. All faculty staffing residents are familiar with the study protocol and can verify the results of the procedure and measurements taken.
10.3. Permitted Concomitant Therapy This section should be consistent with the medication restrictions in the inclusion/exclusion criteria previously listed. Describe how allowed concomitant therapy might affect the outcome (e.g., drug-drug interaction, direct effects on the study endpoints).
N/A
10.4. Rescue Medicine List all medications, treatments, and/or procedures that may be provided during the study for "rescue therapy" and relevant instructions.
N/A, no rescue medicine

11. Study Intervention Discontinuation
11.1. Discontinuation of Study Intervention Describe the criteria for discontinuing the study intervention (e.g., halting rules), including any monitoring test(s) and associated clinical decision point(s). Include reasons for temporary discontinuation of the study intervention (e.g., type and quantity of adverse events), clearly stating the length of time, if applicable, and describe the data to be collected at the time of study intervention discontinuation and approaches for restarting administration of or re-challenging with study intervention.
Study will be discontinued if more than 5% of subjects present an adverse reaction such as infection or material recall. Such a reaction would be extremely rare as the study materials are FDA approved have been on use in the US market for years.

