All of the bone graft material and overlying membrane material will be provided by Geistlich Biomaterials. To eliminate variability that might occur if more than one human donor's tissue is used in the study, all of the DFDBA graft material for all treatment groups will be derived from a single human donor. The DFDBA graft material will be tested for inductivity by the tissue bank (DCI Donor Services Tissue Bank).						
All patients will have a single non-molar tooth extracted. Following extraction, patients will be randomized to one of the 4 treatment groups. Clinical ridge measurements will be made using a custom-made thermoplastic measurement stent, and ridge preservation will be performed using one of the materials listed above, per assigned study arm. After graft placement, the graft material will be covered with a resorbable collagen membrane (Bio-gide) membrane (Geistlich Biomaterials) and the site will be sutured with resorbable sutures without attempt at primary closure.						
Patients will return 1 to 3 weeks after ridge preservation for post-operative evaluation, and thereafter as indicated by clinical findings. Following the 18 to 20-week wound healing period, a core biopsy will be harvested from the site at the time of implant placement. Just prior to the core biopsy, clinical ridge measurements will again be made using the customized measurement stent.						
The core biopsy will be evaluated histomorphometrically for the primary outcome: % vital bone formation. Secondary histologic outcomes include % residual graft material and % "CT/other" (fibrous tissue and marrow space). The histomorphometric						

evaluation will be performed blindly, as the cores being examined will be de-identified as to study arm. In line with our other studies, we will also evaluate the following **secondary clinical outcomes** for each subject: change in ridge width; change in buccal ridge height and change in lingual ridge height.

DETAILED DESCRIPTION OF METHODS:

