Patients will be given the opportunity during the appointment to ask any question that they may have. Following an informational discussion with the prospective subject, consent will be obtained within 2 weeks. This is up to the discretion of the patient. If the patient would like to become a subject for entry into the study, he or she can do so immediately, or can consider it for up to 2 weeks (must be prior to extraction).

Visit 2 – Extraction with ridge preservation using one of the 4 materials described above. All materials are FDA approved and will be used in an FDA approved manner. If the patient has agreed to participate in the study, informed consent will be obtained and documented on a written consent form. If not, standard care treatment will be provided to the patient, and the patient would not be included in the study. Patients will be assigned to one of the 4 groups by randomization with a 1:1 ratio.

On the day of the planned tooth extraction, the medical history will be updated.

Pregnant women or women intending to become pregnant during the study period: Prior to dental surgery, females of child-bearing age are asked verbally if there is any possibility that they are pregnant. If not, we proceed with surgery and no pregnancy test is done. If the woman states that there is a possibility that she is pregnant, an over-the-counter urine pregnancy test to rule pregnancy in or out will be provided. Use of the urine pregnancy test is only done if she says she may be pregnant. [If needed: Urine pregnancy test will be provided to female subjects in the graduate periodontics clinic of UTHSCSA and a negative result is required to enter the study.]

Prior to extraction, impressions of the arch with the tooth to be extracted in place will be taken and poured in stone to obtain initial study casts (research). A clear suck-down resin measuring stent will be fabricated in the laboratory to allow standardization of the location of clinical measurements of ridge width and height through small holes that will be placed in the stent at the time of tooth extraction.

A pre-operative periapical radiographic image will be taken before the extraction as per standard care (if not already available).

At the time of surgery, local anesthesia will be administered. Conscious sedation will be administered according to patient need and investigator preference, per standard care. Buccal and lingual flaps will be minimally reflected to a point up to 3mm apical to

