The socket will be thoroughly debrided, the patient will be randomized to one of the study groups (Group 1, 2, 3 or 4), and the graft material will be placed in the extraction socket to a level even with the interproximal bone height of the mesial and distal aspects of the socket. The material will be condensed into the socket gently. In all sockets, a BioGide resorbable collagen membrane will be placed over the socket and graft material to retain the material in place. The edges of the membrane will be “tucked” under the flap margins to help with membrane retention, and the flaps will be sutured. Primary closure of the flaps will not be performed, per standard care. Flaps will be stabilized with chromic gut sutures, per standard care.

Visit 3 - Post-operative visit

The post-operative visit after extraction/ridge preservation will be scheduled approximately 3 weeks (± 1 week) after the procedure. At this visit a clinic exam will be performed to evaluate healing. Any remaining sutures will be removed. If needed, an optional POT visit may be scheduled before this visit, per standard care and as determined by patient need.

Visit 4 - Pre-implantation:

Approximately 3-4 months after the extraction, the patient will be seen for pre-implant evaluation, per standard care. If needed, a cone beam computed tomography (CBCT) scan will be taken per standard care.

Prior to surgery, pregnancy status will be confirmed verbally. An over-the-counter pregnancy test will be provided if pregnancy status is unknown or suspected (research). A negative result is required to continue being in the study.

Visit 5 - Implant placement:

Prior to surgery, pregnancy status will be confirmed verbally. An over-the-counter pregnancy test will be provided if pregnancy status is unknown or suspected (research). A negative result is required to continue being in the study.

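### Section 10.1 draws the allocation envelope before the surgical appointment, and nothing keeps it sealed until the enrollment decision that Section 5.3 places after extraction and before randomization

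*Combined protocol and SAP*

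**What the plan says.** Section 10.1 describes paper slips in envelopes, 30 for each of the four groups. On concealment it says "The envelopes will be sealed and shuffled", and on timing "The faculty staffing the procedure will draw an envelope from the stack prior to the surgical procedure appointment". It gives no time of opening and does not name who opens the envelope.

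Section 5.3 places randomization later. Its design summary says "Following extraction, patients will be randomized to one of the 4 treatment groups". Its Visit 2 methods give the order in more detail:

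- Before surgery: "On the day of the planned tooth extraction, the medical history will be updated". Women of child-bearing age are asked about pregnancy, with a urine test if it is possible.
- Before extraction, baseline ridge width and height are measured through the stent.
- After extraction: "Following tooth extraction, a final determination of enrollment into the study will be conducted based on the integrity of the buccal bone wall plate". The rule for leaving is "Conversely, if the buccal plate integrity has not been maintained (bony dehiscence >50%) the patient will be exited from the study".
- Then: "The socket will be thoroughly debrided, the patient will be randomized to one of the study groups (Group 1, 2, 3 or 4"). Grafting comes next.

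Section 5.3 also states that the surgeon cannot be blinded. Section 10.1 limits blinding to the histomorphometric measurements. Section 12.3 analyses participants who complete the study intervention.

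**The concern.** The enrollment decision on the buccal plate falls after the draw in 10.1 and before the randomization in 5.3. If the envelope is opened when drawn, the operating team may know the arm while deciding whether a site is above or below the 50% limit. Exit could then depend on the arm, and those who exit do not contribute to the vital bone comparison. Section 10.1 argues that the surgeon need not be blinded because the outcome is histologic. That answers the question of outcome assessment but not the question of who enters: the blinded reader sees only cores from patients who stayed in.

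The exit decision would also be hard to audit. Section 5.3 asks for the following: "After extraction, the number of bony walls in each socket will be recorded along with the presence of any bony dehiscences or fenestrations". It does not ask for the depth of a dehiscence as a share of socket depth, which is the quantity the rule uses.

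A second gap exists even if every envelope stays sealed. The draw precedes the medical-history update, any pregnancy test and the dehiscence decision, so an envelope can be drawn for a patient who is never entered. No rule says whether it is discarded or returned.

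A lesser point is that the arm could be known at the baseline ridge measurements. These serve secondary outcomes and are taken through a fixed stent, and later opening would protect only the baseline reading.

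**Working it through.** **Sequence.** The plan states no figure on this point, so the first check is the order of events.

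- Section 10.1: envelope drawn, then surgical appointment.
- Section 5.3: history update and pregnancy check, baseline ridge measurements, extraction, enrollment decision, debridement, randomization, graft.

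Read together, every pre-graft check falls between the draw and the randomization. Nothing elsewhere states when the envelope is opened.

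**Possible size if the envelope is opened at the draw.** This is illustrative. The documents give no exit rate, no direction of selective exit and no link between dehiscence and vital bone.

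Inputs from the plan: SD 15 points, 20% attrition and 30 enrolled per group (Section 12.2); two-sided 5% tests and pairwise t-tests (Section 12.4). Analysed per arm: 30 × 0.8 = 24.

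Assumptions: a share p of one arm exits selectively, and those sites have g points less vital bone than the sites that stay. There is no true difference between arms.

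If the sites that stay have mean M, the full arm has mean (1 − p)M + p(M − g) = M − pg. Removing the exits therefore raises that arm's mean by p × g. For g = 15:

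- 0.05 × 15 = 0.75 points
- 0.10 × 15 = 1.5 points
- 0.20 × 15 = 3.0 points

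The rejection rate comes from the noncentral t distribution with noncentrality p × g / SE.

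- *Equal arms*, exits replaced: 24 v 24, SE = 15 × √(2/24) = 4.33, df = 46.
- *Depleted arm*, exits not replaced and on top of the 20% attrition: 24 × (1 − p) = 22.8, 21.6 or 19.2 v 24; SE = 4.39, 4.45 or 4.59; df = 44.8, 43.6 or 41.2.

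| Gap g | Arms | p = 5% | p = 10% | p = 20% |
|---|---|---|---|---|
| 15 | equal | 5.3% | 6.3% | 10.4% |
| 15 | depleted | 5.3% | 6.3% | 9.8% |
| 10 | depleted | 5.1% | 5.6% | 7.1% |
| 5 | depleted | 5.0% | 5.1% | 5.5% |

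With equal arms and p = 20%, the 10-point and 5-point gaps give 7.4% and 5.6%. A simulation of 100,000 trials with 19 v 24 and a shift of 3.0 also gave 9.8%.

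**Envelope count.** There are 4 × 30 = 120 envelopes for 120 planned patients. If 5% to 20% were drawn for patients not entered and then discarded, 120 × 0.05 = 6 to 120 × 0.20 = 24 would be lost. That leaves 114/4 = 28.5 down to 96/4 = 24 per arm on average before attrition, possibly unequally. Returning an opened envelope to the stack would weaken concealment.

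**The case against.** The sections need not conflict. Section 10.1 times the draw of a sealed envelope, and Section 5.3 times the act of randomizing. Drawing early and opening after debridement satisfies both, and opening at the draw would sit badly with 5.3. This is a fair reading, and under it there is no bias by this route. But the seal is mentioned only where the preparation of the envelopes is described, and the text does not carry it forward to the enrollment decision. Concealment would rest on unwritten practice.

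The exit rule is a fixed threshold applied to every arm, so bias needs sites near 50% to be misjudged in an arm-dependent direction. This stands, and it makes the 20% column an extreme. A 15-point gap equals both the SD and the target difference in Section 12.2, and no document supports either the rate or the gap.

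The documents do not say who opens the envelope, who judges the dehiscence, or whether the faculty member who draws it also operates. This also stands: the plan permits the arm to be known at the decision but does not show that it will be. Likewise, leaving out patients who exit before allocation is ordinary practice and matters only if the arm was already known.

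Finally, moving the draw itself is more than is strictly needed; an instruction to keep the envelope sealed, with a rule for unused ones, would do. That is correct as a minimum. Drawing after the decision achieves both at once and matches 5.3.

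**Conclusion.** The concern holds and should be fixed. Section 10.1 draws the envelope before the appointment, Section 5.3 randomizes after the enrollment decision, and no text keeps the envelope sealed in between or says what becomes of one drawn for a patient who is not entered. Confidence is high that the text is missing; that bias would follow is conditional on early opening and arm-dependent exit.

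On the assumptions above, a pairwise type I error of 5% becomes at most about 5.3% when 5% of one arm exits selectively, at most about 6.3% at 10%, and about 10% only when 20% exits with a gap of a full SD. The distortion is small unless selective exit is both common and strongly tied to outcome. The case for changing the text is that the safeguard is basic and costs almost nothing.

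**What to change.** Bring Section 10.1 into line with Section 5.3. State that:

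- the envelope is drawn and opened only after the baseline ridge measurements and the dehiscence determination are recorded and the socket is debrided;
- the record of that determination includes dehiscence depth as a share of socket depth;
- a patient who fails any check before that point uses no envelope;
- the number exited before randomization is reported.

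If the early draw must stay for practical reasons, the minimum is to require that the envelope remain sealed until the dehiscence decision is recorded, with a written rule for envelopes not used. Opaque, sequentially numbered envelopes are optional good practice.

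The cost is one or two sentences in 10.1 and one recorded item. All four products must be at the chairside. Sections 9.3 and 9.4 describe them as stored at room temperature and used off-the-shelf, so this needs no special preparation. Visits, sample size, analysis and the exit rule itself do not change.
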